9.2 MEASUREMENT OF TREATMENT COMPLIANCE

Dosing compliance for a specified period is defined as the total number of capsules actually taken by a patient during that period divided by the number of capsules prescribed that were expected to be taken during the same period multiplied by 100. The total number of capsules actually taken during a specific period is calculated as the number of days in that period multiplied by the number of capsules taken each day during that period. The number of capsules expected to be taken for a specific treatment period will be calculated by multiplying the number of days in that period by the number of capsules to be taken per day. This information will be obtained from the IP record of the patient's eCRF. Descriptive statistics for IP compliance will be presented by treatment for each period between 2 consecutive visits, as well as for the period from the first dose of DB IP actually taken to the last dose of DB IP actually taken from the Safety Population.

Cariprazine
RGH-MD-25 – Statistical Analysis Plan
Amendment #3 – 23 November 2022

Descriptive statistics (n, mean, standard deviation, median, minimum and maximum) for OL IP compliance will be presented overall for each period between 2 consecutive visits, as well as for the entire OLTP for the OL Safety Population. Descriptive statistics (n, mean, standard deviation, median, minimum and maximum) for DB IP compliance will be presented by treatment group for each period between 2 consecutive visits, as well as for the entire DBTP for the DB Safety Population.

10.0 EFFICACY ANALYSES

All efficacy analyses for the OLTP will be performed using the OL ITT Population, unless stated otherwise. Baselines for efficacy parameters in the OLTP will be defined as the last nonmissing efficacy assessment before the first dose of OL IP.

All efficacy analyses for the DBTP will be performed using the DB ITT Population, unless stated otherwise. Baselines for the additional efficacy parameters in the DBTP will be defined as the last nonmissing efficacy assessment before the first dose of DB IP.

All statistical tests will be 2-sided hypothesis tests performed at the 5% level of significance and all confidence intervals (CIs) will be 2-sided 95% CIs, unless stated otherwise.

To accommodate the flexible duration of the OLTP, the derived visits in the DBTP will be named as Week *i* post randomization (or DB Week *i*) for a specific Week *i* after the first dose of the DB study medications. The total exposure to IPs for patients in Week *i* post randomization will vary because of the flexible OLTP. The detailed week-mapping windows is provided in Section 16.1.

10.1 PRIMARY EFFICACY PARAMETER

The primary efficacy parameter is the time to first relapse of any mood episode during the DBTP. The time to first relapse is defined as the number of days from the randomization date to the first relapse date. Relapse during the DBTP will be defined as meeting 1 or more of the following criteria:

- YMRS total score ≥ 17
- MADRS total score ≥ 20
- CGI-S ≥ 4
- Initiation of treatment with a mood stabilizer, antidepressant, antipsychotic agent, or with a benzodiazepine that exceeds the protocol-specified allowance or duration (ie, more than 2 mg/d of lorazepam equivalent or for more than 3 consecutive days) to treat worsening mood symptoms as judged by the clinical impression of the investigator
- Psychiatric hospitalization
- Exacerbation of illness as judged by clinical impression of the investigator (eg, clinically significant agitation, suicidal or homicidal ideations)

For patients who meet the above relapse criteria will categorize the relapse event(s) as manic or depressive event(s), with or without mixed features. Patients who did not meet the above relapse criteria will be censored at the time of completion or discontinuation from the DBTP.

The primary efficacy analysis is to evaluate the time to first relapse of any mood episode in bipolar I disorder patients who responded to OLTP with cariprazine.

The primary null hypothesis is that the distribution of the time to first relapse for each of the cariprazine 3.0 mg/d and 1.5 mg/d treatment groups is not different from that for the placebo treatment group. The alternative primary hypothesis is that the distribution of the time to first relapse for each of the cariprazine 3.0 mg/d and 1.5 mg/d treatment group is different from that for the placebo treatment group.

The hypothesis testing will compare the time to relapse between each cariprazine group and placebo group using the log-rank test stratified by modified index episode (manic or depressive) and region (US, non-US) for the DB ITT population. To derive the modified index episode, the manic index episode(s) with or without mixed features will be classified as manic episode(s); depressive index episode(s) with or without mixed features will be classified as depressive episode(s). Estimates of the hazard ratio (HR) and 95% confidence intervals will be based on the Cox proportional hazards model with treatment group as the covariate stratified by modified index episode (manic or depressive) and region (US, non-US). The Kaplan-Meier estimates for the cumulative distribution of the relapse rate for each treatment group will be provided.

Per the protocol, relapses are collected within a double-blind treatment period that lasts with a maximum of 39 weeks (or 273 days + 3 days visit time window), hence all survival analyses will censor data at 276 days.

The primary hypotheses for cariprazine 3.0 mg/d and 1.5 mg/d treatment groups versus placebo will be tested sequentially in order to control the overall Type I error rate. The comparison of cariprazine 3.0 mg/d versus placebo will be tested first at two-sided 0.05 significance level, and only when it is significant, the comparison of cariprazine 1.5 mg/d versus placebo will be tested also at the two-sided 0.05 significance level. This testing strategy controls the overall Type I error rate at 0.05 significance level.

Two sensitivity analyses will be performed to assess the robustness of the primary analysis results to the possible violation of the noninformative censoring assumption.

The first sensitivity analysis will be based on the delta-adjusted method examined by Zhao et al. (2014), which specifies that the hazard of having an event for subjects who discontinued before the time point is increased relative to the hazard for subjects who continued beyond the time point for the experimental treatment group. The delta-adjustment will be gradually increased from zero until reaching the tipping point when the statistical significance of the primary efficacy endpoint is overturned, and the plausibility of the magnitude of delta-adjustment needed for reaching the tipping point will be subject to clinical scrutiny.

The second sensitivity analysis is an extension of the placebo-based pattern mixture model proposed by Lu (2014, 2015). The placebo-based pattern mixture model assumes that patients who discontinued from the cariprazine treatment groups would have disease progression after discontinuation similar to that of placebo. The extended placebo-based pattern mixture model uses a sensitivity parameter to characterize the gradual deviation from the noninformative censoring underlying the primary analysis toward the informative censoring underlying the placebo-based pattern mixture model. The extended placebo-based pattern mixture model sensitivity analysis for time-to-event data is described as follows:

Let $h_0(t)$ denote the baseline hazard function associated with the placebo group. Let β_1 and β_2 denote the treatment effects in terms of log HRs under noninformative censoring for cariprazine 1.5 mg/d versus placebo and cariprazine 3.0 mg/d versus placebo, respectively. The hazard functions associated with the cariprazine 1.5 and 3.0 mg/d groups under noninformative censoring are thus given by $h_1(t) = h_0(t) \exp(\beta_1)$ and $h_2(t) = h_0(t) \exp(\beta_2)$, respectively. Consider the extended placebo-based pattern mixture model sensitivity analysis. For the placebo group, we assume that patients with premature discontinuation would have comparable experience after discontinuation to their counterparts without premature discontinuation. For the cariprazine treatment groups, each dropout time point for cariprazine patients defines a missing data pattern, and we assume that patients with premature discontinuation would have disease progression after discontinuation somewhere between their counterparts without premature discontinuation and patients in the placebo group. Specifically, we assume that $h_1(t) = h_0(t) \exp((1-\phi)\beta_1)$ and $h_2(t) = h_0(t) \exp((1-\phi)\beta_2)$ for $t > C$, where C denotes the time of premature discontinuation. The sensitivity parameter $\phi \in [0,1]$ characterizes the gradual deviation from the noninformative censoring with $\phi = 0$ toward the informative censoring underlying the placebo based pattern mixture model with $\phi = 1$. A multiple imputation approach will be used to implement the extended placebo-based pattern mixture model.

Sample SAS programs for primary efficacy analysis and sensitivity analyses are provided in [Appendix I](#) and [Appendix II](#).

The analysis for primary efficacy parameter will be performed within each category of the following, and the corresponding Kaplan-Meier curves will be provided:

- Age group (< 45 years, \geq 45 years).
- Sex (male, female)
- Race (white, all other races)
- Region (US, Non-US)
- Modified index episode (manic or depressive)

Manic episode with mixed features or depressive episode with mixed features is classified as manic or depressive episodes, respectively.

Kaplan-Meier curves of cumulative rate of first relapse with manic episode with or without mixed features during the DBTP, and Kaplan-Meier curves of cumulative rate of first relapse with depressive episode with or without mixed features during the DBTP will be generated.

Additional sensitivity analysis for the primary endpoint, time to first relapse of any mood episode, will be conducted for the DB ITT population, censoring ongoing participants in Russia and Ukraine as of 24Feb2022, and will be analyzed using the log-rank test stratified by modified index episode and region. Any relapse events in Russia and Ukraine on or after 24Feb2022 will not be included and all ongoing participants in those two countries will be considered ‘lost’ as of that date.

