7.2.3 Other Efficacy Variables

Additional efficacy parameters include:

- Change from baseline in YMRS total score by visit during OL and DB period
- Change from baseline in MADRS total score by visit during OL and DB period
- Change from baseline in CGI-S score by visit during OL and DB period
- CGI-I score by visit during OL and DB period
- Change from baseline in PSP score by visit during OL and DB period

Additional efficacy parameters only for the DB treatment period include:

- Time to manic episode
- Time to depressive episode

Manic episode with mixed features or depressive episode with mixed features are classified as manic or depressive episodes, respectively.

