7.3.3 Other Efficacy Analyses

The overall relapse rate, as well as the relapse rates for sub-categories of interest including manic episode and depressive episode will be presented.

Time to early discontinuation for any reason during the DB treatment period for the ITT population will be analyzed.

These efficacy parameters will be analyzed using the same method used to analyze the primary efficacy variable.

The following continuous efficacy variables will be summarized by visit for the OL and DB treatment periods separately for the corresponding ITT populations. For the DB treatment period, the variables for YMRS, MADRS, CGI-S, and CGI-I will be analyzed by using a mixed-effects model for repeated measures (MMRM) with treatment group, region (US and non-US), modified index episode strata (manic or depressive), visit, and treatment group-by-visit interaction as fixed effects and the baseline value and baseline-by-visit interaction as the covariates. An unstructured covariance matrix will be used. The Kenward-Roger approximation will be used to estimate denominator degrees of freedom.

Descriptive statistics will be provided at each assessment time point by treatment group for the change from baseline in PSP score.

For Open-label Treatment Period

- Change from baseline in YMRS total score by visit
- Change from baseline in MADRS total scores by visit
- Change from baseline in CGI-S score by visit
- CGI-I score by visit
- Change from baseline in PSP score by visit

For Double-blind Treatment Period

- Change from DB baseline in YMRS total score by visit
- Change from DB baseline in MADRS total score by visit
- Change from DB baseline in CGI-S score by visit
- CGI-I score by visit
- Change from DB baseline in PSP score by visit

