8.9 Withdrawal Criteria

It is the right and the duty of the investigator or subinvestigator to stop treatment in any case in which emerging effects are of unacceptable risk to the individual patient. In addition, the investigator or subinvestigator is to stop treatment of any patient with unmanageable factors that may interfere significantly with the trial procedures and/or the interpretation of results.

A patient must be discontinued from the study for any of the following reasons:

1. The patient fails to achieve remission by Week 6 or stability by Week 8 of the OL treatment period;

- 2. After stability criteria (Section 4.5) have been met, if there is a lack of ongoing stability as evidenced by an excursion event of YMRS total score of \geq 17 and/or MADRS total score of \geq 20, or CGI-S \geq 4;
- 3. The patient initiated treatment with a mood stabilizer, antidepressant, antipsychotic agent, or with a benzodiazepine that exceeds the protocol-specified allowance or duration (ie, more than 2 mg/d of lorazepam equivalent or for more than 3 consecutive days) to treat worsening mood symptoms;
- 4. The patient required or initiated hospitalization for his/her psychiatric symptoms (excluding the discretionary hospitalization stay which is to end no later than Visit 3 [Day 8] of the OL treatment period or extension of the initial hospitalization described in this protocol);
- 5. At the end of the OL treatment period, the patient does not meet all criteria to enter the DB treatment period (eg, patient is unable to tolerate cariprazine 3.0 mg/d);
- 6. Positive UDS after enrollment, confirmed by retest at next scheduled visit; for exceptions see Exclusion Criterion 6(b) and Section 4.8.3;
- 7. The patient meets the criteria for relapse of a mood episode during the DB treatment period;
- 8. The patient experiences 1 of the following elevated liver enzyme conditions, which is confirmed by repeat testing:
 - ALT or AST $> 3 \times$ ULN and total bilirubin $> 2 \times$ ULN,
 - ALT or AST $> 8 \times ULN$,
 - ALT or AST $> 5 \times ULN$ for more than 2 weeks,
 - ALT or AST > 3 × ULN with the appearance of jaundice, worsening of fatigue, nausea, vomiting, right upper quadrant pain or tenderness, fever, rash, or eosinophilia.
- 9. The patient has an absolute neutrophil count of < 1000 per mm³ and, after repeat testing within 24 hours of awareness, the values are not normalized or are not increasing;
- 10. A female patient becomes pregnant during treatment.

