10.3 ADDITIONAL EFFICACY PARAMETERS

The overall relapse rate, as well as the relapse rates for sub-categories of interest including modified manic episode and modified depressive episode will be presented.

Time to early discontinuation with any reason (including relapse) during the DBTP for the DB ITT population will be analyzed using the same method used to analyze the primary efficacy variable.

For the following continuous efficacy variables, the change from baseline refers to the change from OL baseline during the OLTP, and the change from DB baseline during the DBTP, unless stated otherwise.

For Open-label Treatment Period

- Change from baseline in YMRS total score by visit
- Change from baseline in MADRS total scores by visit
- Change from baseline in CGI-S score by visit
- CGI-I score by visit
- Change from baseline in PSP total score and sub-domain score by visit

For Double-blind Treatment Period

- Change from DB baseline in YMRS total score by visit
- Change from DB baseline in MADRS total score by visit
- Change from DB baseline in CGI-S score by visit
- CGI-I score by visit
- Change from DB baseline in PSP total score and sub-domain score by visit

Descriptive statistics (n, mean, standard deviation, median, Q1, Q3, minimum and maximum) for additional efficacy parameters will be provided by visit for the OL ITT population and the DB ITT population using both last-observation-carried forward (LOCF) and observed cased (OC) approaches. LOCF approach will be used to impute missing postbaseline values. Imputation of missing values will be done for the OLTP and the DBTP separately.

For the DBTP, the additional efficacy parameters will be analyzed by using a mixed-effects model for repeated measures (MMRM) with treatment group, region (US and non-US), modified index episode strata (manic or depressive), visit, and treatment group-by-visit interaction as fixed effects and the baseline value and baseline-by-visit interaction as the covariates. An unstructured covariance matrix will be used. The Kenward-Roger approximation ([Kenward and Roger, 1997](#)) will be used to estimate denominator degrees of freedom. The analysis will be performed based on post-DB baseline scores using only the OC without imputation of missing values. Least squares mean and their standard errors based on the MMRM analysis will be plotted by treatment group and visit.

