APPENDIX I. SAS PROGRAM FOR PRIMARY EFFICACY ANALYSIS

The primary efficacy analysis for time to relapse include (1) the log-rank test and (2) the Cox proportional hazards model with treatment group and modified index episode (manic or depressive) as the covariate. The sample SAS code for these analyses are provided below. Note in the dataset adtte (DB ITT population), variables trt02pn and trt02p are for the double-blind treatment group, episode is for the modified index episode, aval is for the time (days) to censor/relapse, and cnsr is for the status of censored (=0) or relapsed (=1).

(1) SAS program for log-rank test comparing treatment groups trt02pn=0 and =1:

```
proc lifetest data=adtte method=km;
  strata episode region/test=logrank group=trt02p diff=control('Placebo');
  time aval * cnsr(0);
run;
```

(2) SAS program for Cox proportional hazard model:

```
proc phreg data=adtte;
  class trt02p (ref= 'Placebo') episode(ref='depressive') region;
  model aval * cnsr(0)= episode region trt02p/rl;
  contrast ' cariprazine 1.5 mg/d vs placebo Episode=depressive'    trt02p 1 0  episode 0/
estimate=exp e;
  contrast ' cariprazine 3.0 mg/d vs placebo Episode=depressive'    trt02p 0 1  episode 0/
estimate=exp e;
  contrast ' cariprazine 1.5 mg/d vs placebo Episode=manic'      trt02p 1 0  episode 1/ estimate=exp e;
  contrast ' cariprazine 3.0 mg/d vs placebo Episode=manic'      trt02p 0 1  episode 1/ estimate=exp e;
  ods output parameterestimates=pvval;
run;
```

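### The two exploratory Kaplan-Meier figures of first manic and first depressive relapse have no rule for other-pole relapses; if these are censored, each figure overstates the rate it names

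*SAP*

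**What the plan says.** SAP section 10.1 calls for two sets of curves. The manic set is described as "Kaplan-Meier curves of cumulative rate of first relapse with manic episode with or without mixed features during the DBTP". A parallel request covers the other pole, in the same terms but for depressive relapse. SAP Appendix IV records both as added in Amendment #3 for further exploration of the data. No test is attached to them. They are separate from the Kaplan-Meier curves by modified index episode, which the same section requests as a subgroup display.

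No text in either document says what happens in the manic figure to a patient whose first relapse is depressive, or the reverse:

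- SAP 10.1 gives one patient-level censoring rule: "Patients who did not meet the above relapse criteria will be censored at the time of completion or discontinuation from the DBTP". A patient with an other-pole relapse did meet the criteria, so the rule does not reach that patient.
- SAP 10.1 also cuts all survival data at day 276. This is administrative only.
- SAP Appendix I describes the status variable for time to relapse as binary, censored or relapsed, with no event type.
- Protocol section 7.2.3 lists "Time to manic episode" and the depressive counterpart. Section 7.3.3 says "These efficacy parameters will be analyzed using the same method used to analyze the primary efficacy variable", again without a rule for the other pole.
- SAP section 10.3 separately promises "relapse rates for sub-categories of interest including modified manic episode and modified depressive episode".

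Protocol section 8.9 lists, among the reasons for mandatory discontinuation, "The patient meets the criteria for relapse of a mood episode during the DB treatment period". Protocol section 7.5 likewise follows patients only until dropout, relapse or 39 weeks. Neither document mentions competing risks or cumulative incidence.

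**The concern.** Because any relapse ends participation, a first manic and a first depressive relapse are competing events. The SAP names the quantity to be shown as a cumulative rate of first relapse of each type. Kaplan-Meier with the other pole censored does not estimate that quantity. It estimates what would accumulate if other-pole relapse never removed anyone, on the further assumption that those removed would have gone on to have the pole of interest at the same rate as those who stayed.

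Readers will take each figure as the share of patients whose first relapse was manic, or depressive. Read that way, the two figures would not add up to the trial's own overall Kaplan-Meier curve. The pole-specific relapse rates in SAP 10.3 are only a partial cross-check. If they are simple proportions, dropout pulls them below the true rate while censoring pushes the curve above it.

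**Working it through.** **Inputs from the documents.** SAP section 14.0: placebo relapse 35% at Week 39, hazard ratio 0.42, 26% early discontinuation for other reasons, 126 patients per arm, about 75 events.

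**Assumptions not in the documents.** Constant hazards; independent exponential dropout; manic share of placebo relapses *f* from 20% to 80%; hazard ratio equal for both poles unless stated.

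**Reproducing the plan's event count.** Placebo cumulative hazard H = −ln(0.65) = 0.4308. Cariprazine relapse = 1 − 0.65^0.42 = 16.6%. Dropout hazard d = −ln(0.74) = 0.3011. Expected events per arm = 126 × h/(h+d) × (1 − e^−(h+d)): placebo 38.5, each cariprazine arm 18.1, total 74.7 against the stated 75. The planning inputs are therefore read correctly.

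**Curve against rate.** For a pole with cumulative hazard h out of a total T:

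- One minus Kaplan-Meier, other pole censored: 1 − e^−h
- Cumulative incidence: (h/T)(1 − e^−T)

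| Share of the pole plotted | Placebo KM | Placebo true | Cariprazine KM | Cariprazine true | Arm difference overstated by |
|---|---|---|---|---|---|
| 20% | 8.25% | 7.00% | 3.55% | 3.31% | 1.01 |
| 50% | 19.38% | 17.50% | 8.65% | 8.28% | 1.50 |
| 80% | 29.15% | 28.00% | 13.48% | 13.24% | 0.92 |

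The excess is 1.2 to 1.9 points on placebo and 0.2 to 0.4 on cariprazine. The two placebo curves sum to 8.25 + 29.15 = 37.4% at a 20/80 split and to 38.8% at 50/50, against 35%.

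In simulated trials of 126 per arm with 26% dropout (4,000 per setting, pole shares 30%, 50% and 70%), the censored curve never ended below the cumulative incidence. It was strictly above in every placebo arm and in at least 99% of cariprazine arms.

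**Sampling error for scale.** At 50/50 and before dropout, the standard error of the arm difference is √(0.175×0.825/126 + 0.083×0.917/126) = 4.2 points.

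**Unequal hazard ratios (manic share 30% to 70%).**

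- With 0.42 for one pole and 1.0 for the other, the Kaplan-Meier arm difference exceeds the cumulative-incidence difference by 0.8 to 1.1 points.
- With 0.5 and 2.0, the shift is −0.1 to +0.2 points.

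**Effect of the missing rule.** Placebo, 50/50 split, 26% dropout, true rate 17.5%. Here h = 0.2154 per pole, A = 2h + d = 0.7319, p = h/A = 0.2943 and e = e^−A = 0.481.

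| Handling of other-pole relapse | Formula | Plotted rate |
|---|---|---|
| Censored | 1 − e^−h | 19.4% |
| Kept at risk to day 276 | 1 − exp{−[p/(1−p)] ln[1/(p+(1−p)e)]} | 17.3% |
| Excluded | 1 − exp{−[p/(1−p)] ln[((1−p)+pe)/e]} | 21.0% |
| Simple proportion | p(1 − e) | 15.3% |

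Three programmers following the SAP text could thus plot values up to 3.7 points apart from the same data.

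**The case against.** **A separate document may hold the rule.** SAP section 4.0 says that specifications of tables and figures are kept elsewhere, and that document is not available. This limits the claim to what the SAP and protocol state. It does not remove it: the SAP itself names Kaplan-Meier, whose default is to censor, and calls the result a cumulative rate.

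**Appendix I was written for the primary endpoint.** The code in Appendix II selects one parameter from the analysis dataset, so pole-specific records with their own status may exist. That is fair. The binary variable shows only that no event-type code is described.

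**For comparing arms, the choice is partly one of estimand.** With manic hazard ratio 0.42 and depressive 1.0 at 50/50, the censored depressive curves coincide, correctly reflecting an unchanged hazard. Depressive cumulative incidence is 18.6% on drug against 17.5% on placebo, only because fewer patients are removed by manic relapse. This stands, and it is why cumulative incidence should not be the sole pole-specific analysis.

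**The table and figure would disagree anyway.** Of the 4.1-point gap between 19.4% and 15.3%, 17.5 − 15.3 = 2.2 points come from dropout and 1.9 from this issue. That also stands.

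**The practical weight is small.** The figures are exploratory, and the shift in the arm difference is at most about a third of its standard error. This is accepted and sets the priority.

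**Conclusion.** The concern holds in its conditional form. The documents give no rule for other-pole relapses in these figures. If they are censored, each curve is at or above the cumulative rate it is labelled with, and strictly above once an own-pole relapse follows an other-pole relapse in that arm. That direction does not depend on the planning assumptions.

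The size does depend on them. It also rests on an assumed pole split and, for the figures of 1.2 to 1.9 points on placebo and 0.2 to 0.4 on drug, on equal hazard ratios. Overstatement of the arm difference (0.9 to 1.5 points) is likewise conditional and can vanish when the drug's effects on the two poles oppose each other.

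The primary endpoint, its log-rank test, the significance level and the sample size are untouched. This is an optional improvement to two exploratory figures.

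**What to change.** 1. State in SAP 10.1 how a first relapse of the other pole is handled.
2. Present the two figures as Aalen-Johansen cumulative incidence curves with the other pole as competing event (PROC LIFETEST with the EVENTCODE option), using an event-type code derived from the recorded relapse category.
3. If any Kaplan-Meier version is kept, label it cause-specific and not a cumulative rate.
4. If the time-to-manic and time-to-depressive comparisons in protocol 7.2.3 and 7.3.3 are still wanted, write a cause-specific log-rank and Cox analysis into SAP 10.3, which does not now spell one out. Cumulative incidence alone cannot show which pole the drug acts on.

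The cost is two or three SAP sentences, one derived variable and a changed procedure option; item 4, if taken up, adds a short analysis specification. No new data are needed, because the investigator already classifies each relapse as manic or depressive.
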